**3.3 Final Analysis**

Final analysis will be done when all participants complete the extension phase and after database lock.

**4 ANALYSIS POPULATIONS (SETS)**

The following populations will be used during statistical analyses:

- **Screened population:** All participants screened (i.e. who signed the informed consent)
- **Safety population:** All participants who received at least one dose of study medication and have at least one post-baseline safety assessment
- **Intention-To-Treat population (ITT):** All participants who received at least one dose of study medication
- **Modified Intention-To-Treat population (mITT):** All treated participants having at least one baseline and at Month 3 post-baseline assessment of the primary efficacy endpoint

- **Per protocol set (PPS):** All participants in the mITT after exclusion of the participants who had major protocol deviations that could potentially affect the primary efficacy endpoint outcome for the participants
- **PK set (PKS):** All participants who received at least one dose of study medication and have at least one valid and quantifiable concentration in main study phase.

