7.4 Methods and Timing of Assessing, Recording and Analysing Efficacy Data

Laboratory tests for efficacy will be performed centrally. The laboratory methods for assessing efficacy data are listed in [Section 5.3](#). The timing of efficacy assessments is summarised in [Table 1](#). Procedures for recording efficacy data are discussed in [Section 15.1](#) and methods of analyses are discussed in [Section 11.4.4](#).

7.4.1 *Change in Luteinising Hormone and Follicle-stimulating Hormone Serum Concentrations*

These parameters will be analysed centrally, as indicated in [Section 5.3](#). The preparation and storage of samples are described separately in the Laboratory Manual.

7.4.2 *Gonadotropin-releasing Hormone Stimulation Test*

Gonadorelin, a synthetic GnRH (manufacturer to be defined), will be used for gonadotrophin stimulation. Gonadorelin used for GnRH stimulation test will be prepared by the investigator sites.

Blood samples will be collected prior to gonadorelin injection (timepoint T0) and at 30 minutes (T30), 60 minutes (T60) and 90 minutes (T90) (± 5 minutes at each timepoint) after a single i.v. injection of gonadorelin with 2.5 μ g/kg (maximum 100 μ g).

A suppressed LH response to GnRH stimulation test is defined as peak LH ≤ 3 IU/L among the four timepoints (T0, T30, T60 and T90).

The FSH response to GnRH stimulation will be the peak FSH level among the four timepoints (T0, T30, T60 and T90).

7.4.3 *Change in Sex Steroids (Oestradiol and Testosterone Serum Concentrations)*

These parameters will be analysed centrally, as indicated in [Section 5.3](#). The preparation and storage of samples are described separately in the Laboratory Manual.

7.4.4 *Change in Pubertal Stage Using the Tanner Method*

See Pubertal Stages According to the Tanner Method ([Appendix 1](#)) for details.

7.4.5 *Auxological Parameters, Bone Age and Chronological Age Measurements and Gonad Development*

Bone age determination (in years and months) will be performed by X-rays of the hand and wrist and estimated by the Greulich and Pyle method [[Greulich 1959](#)].

Gonad development (uterine length or testis volume) will be determined by type B ultrasound.

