11.3 Significance Testing and Estimations

The observed response rate in global study 2-54-52014-143 was 83.8% (95% CI: 68.0% to 93.8%). With N=28, there is 90% probability that the observed response rate will be within 16 percentage points of the true response rate based on a simulation. Due to the small sample size and potential wider precision of the estimator, the primary endpoint will be summarised descriptively. No formal hypothesis test will be performed.

For the primary efficacy endpoint, the summary statistics of number and percentage of participants and the exact two-sided 90% confidence interval (CI) for a binomial proportion will be computed by SAS® using the exact binomial distributions on the mITT (primary population of analysis), ITT and PP.

For secondary efficacy endpoints related to a change at Month 3 and Month 6 compared to baseline, the descriptive summary statistics (n, mean, SD, median, minimum, maximum) will be calculated on the mITT. In addition, secondary efficacy endpoints may be performed on the PP. Exact two-sided 90% CIs will also be constructed for all secondary endpoints expressed as percentages.

For extension phase efficacy endpoints related to a change at Month 9 and Month 12 compared to baseline, the descriptive summary statistics (n, mean, SD, median, minimum, maximum) will be calculated on the ITT and PP. Exact two-sided 90% CIs will also be constructed for all extension phase efficacy endpoints expressed as percentages.

The analysis results based on the statistical methods above will provide the reference for whether the efficacy of treatment of CPP in children in China has same or similar trend with that in overseas CPP population.

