#### 4.1 Populations Analysed

##### *Main study phase*

The primary efficacy analysis will be performed on the mITT population. Supportive analysis of the primary efficacy endpoints will be based on the ITT and the PP populations.

The secondary efficacy analyses will be based on the mITT population. Supportive analysis of the secondary analyses may be performed on the PP population.

The analyses of safety data will be performed based on the Safety population.

The analyses of PK data will be performed based on the PK population.

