##### Handling of Dropouts or Missing Data

A NRI method will be used for missing LH response and FSH response at month 3 or month 6. For any missing value of LH response and FSH response at month 3 or month 6, a Non-response value will be imputed.

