**5.7.2.2 Primary Analysis**

For the primary efficacy endpoint, the summary statistics of number and percentage of participants and the exact two-sided 90% confidence interval (CI) for a binomial proportion will be computed by SAS® using the exact binomial distributions on the mITT.

The SAS code to be used could be presented in Appendix A1.

A listing will be provided including all participants with missing values for the primary endpoint. For these participants, the listing will provide all observed data related to the primary endpoint i.e. all measurements recorded prior to the missing value, any measurements recorded after the missing value, important baseline characteristics, the reason for study discontinuation and the timing of study discontinuation. The listing will also provide the imputed value(s) (if applicable) used in the primary analysis and any sensitivity analyses.

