**5.7.2.3 Sensitivity Analysis**

Sensitivity analyses will be conducted to further explore the primary efficacy endpoint with the same statistical method using NRI method on the ITT set.

A PPS population will also be used to explore the primary efficacy endpoint with the same statistical method.

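### Does the non-responder rule for a missing Month 3 LH response fail because the primary mITT set leaves out untested children?

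*SAP*

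**What the plan says.** SAP 4 defines the mITT as "All treated participants having at least one baseline and at Month 3 post-baseline assessment of the primary efficacy endpoint", and Protocol 11.1 uses the same definition. The per-protocol set is drawn from the mITT. The ITT set is everyone who received a dose. SAP 4.1 states: "The primary efficacy analysis will be performed on the mITT population".

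On missing data, SAP 5.7.1.2 (Handling of Dropouts or Missing Data) says: "For any missing value of LH response and FSH response at month 3 or month 6, a Non-response value will be imputed". It names no analysis set. SAP 5.7.2.3 does name one: the primary endpoint is re-analysed "with the same statistical method using NRI method on the ITT set". Protocol 11.3 has the rate and exact 90% interval computed "using the exact binomial distributions on the mITT (primary population of analysis), ITT and PP".

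SAP 5.7.2.2 plans a listing of every child whose primary endpoint is missing and adds: "The listing will also provide the imputed value(s) (if applicable) used in the primary analysis and any sensitivity analyses". SAP 5.2 plans a summary of each analysis set with reasons for exclusion.

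Protocol 7.4.2 takes peak LH over four samples: the one before gonadorelin (T0) and those at 30, 60 and 90 minutes. Protocol Table 5 and SAP Table 1 list only 30, 60 and 90 minutes. No readable text gives a minimum number of samples.

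**The concern.** Someone who reads only SAP 5.7.1.2 would take the primary Month 3 rate to be a non-responder-imputed rate. For untested children it is not: they leave both numerator and denominator, and the rate is an observed-case rate. The mention in SAP 5.7.2.2 of imputed values in the primary analysis strengthens the wrong impression.

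A second gap sits inside the mITT. If a child misses one of the timed samples and the rest are at or below 3 IU/L, three readings are open: not an assessment (the child is excluded), an assessment with a missing response (scored as failure), or a response judged on the available samples. The study is open-label, so a choice made after seeing results could be questioned.

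The primary rate will be set beside the 83.8% observed in the global study (Protocol 11.3). Depending on the set, the Chinese estimate could fall on either side of that figure.

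**Working it through.** **The plan's own sizing.** Inputs from Protocol 11.2: expected rate 90%, null 70%, exact one-sided 0.05, power 85%, dropout 10%. The smallest qualifying n is 28 with success at 24 or more: P(X ≥ 24 | 28, 0.7) = 0.047 and P(X ≥ 24 | 28, 0.9) = 0.858. Dropout: 28/0.9 = 31.1, rounded up to 32. The plan's figures reproduce. They size the study on 28 evaluable children, which matches an mITT primary analysis.

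**Where the rule acts.**

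| Situation | mITT (primary) | Per-protocol | ITT sensitivity |
|---|---|---|---|
| No Month 3 test | child not in set | child not in set | non-response |
| No Month 6 test, Month 3 test done | non-response | non-response, if in set | not planned at Month 6 |

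The rule has work to do at Month 3 in the ITT and at Month 6 in the mITT. It is general, and SAP 5.7.2.3 supplies the set for Month 3.

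**Untested children.** With 32 treated, m untested and x responders, the gap is x/(32 − m) − x/32. The counts m are assumptions; x is chosen so that about 90% of tested children respond. Intervals are exact (Clopper-Pearson) 90%.

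| m | mITT | ITT, non-responder imputation | Gap (points) |
|---|---|---|---|
| 1 | 28/31 = 90.3% (76.8 to 97.3) | 28/32 = 87.5% (73.6 to 95.6) | 2.8 |
| 2 | 27/30 = 90.0% (76.1 to 97.2) | 27/32 = 84.4% (69.9 to 93.6) | 5.6 |
| 3 | 26/29 = 89.7% (75.4 to 97.1) | 26/32 = 81.3% (66.3 to 91.5) | 8.4 |
| 4 | 25/28 = 89.3% (74.6 to 97.0) | 25/32 = 78.1% (62.8 to 89.3) | 11.2 |

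If about 83.8% of tested children respond, the gaps are 2.6, 5.2, 7.8 and 10.3 points (26/31, 25/30, 24/29 and 23/28, each against the same numerator over 32). Planned dropout is 32 × 0.10 = 3.2, about 3 children; the documents do not say how many would leave before Month 3. Every interval in the table contains 83.8%.

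**Partial tests.** Any value above 3 IU/L that counts towards the peak already makes the child a non-responder, so only a partial test with all available values at or below 3 is undecided. Suppose 1 of 32 tests is of this kind and 28 of the other 31 children respond:

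- excluded: 28/31 = 90.3%
- scored as missing, hence failure: 28/32 = 87.5%
- judged on available samples: 29/32 = 90.6%

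The range is 1/32 = 3.1 points. With two such tests and 27 of the other 30 responding, the results are 27/30 = 90.0%, 27/32 = 84.4% and 29/32 = 90.6%, a range of 2/32 = 6.25 points.

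**What changing the primary set would cost.** Suppose all the 10% dropout fell before Month 3 and missing tests counted as failures. The expected rate is then 0.9 × 0.9 = 81%. In a notional exact test against 70% with n = 32, the cut-off is 28 (P(X ≥ 28 | 32, 0.7) = 0.019) and power is P(X ≥ 28 | 32, 0.81) = 0.246. No test is planned, but this shows that the sizing was not built for an all-treated analysis with failures imputed.

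**The case for a change.** The strongest case for a change is that the primary figure is the one readers remember. On these illustrations it sits above the conservative estimate, and the missing sentences would be cheap to add. A supportive ITT analysis does not settle partial tests, which can affect all three sets. With several timed blood draws in young children, a missed sample is foreseeable.

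The factual part of this stands: for wholly missing tests the primary rate is observed-case, and the partial-test rule is not in the readable text. The rest is weaker.

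- The primary rate is normally at or above the imputed ITT rate, but not by necessity. The mITT also requires a baseline assessment, so a treated child with a Month 3 response and no baseline value would count only in the ITT. With assumed counts, that could give 27/31 = 87.1% against 28/32 = 87.5%. It is unlikely, because stimulated LH is an entry criterion.
- A higher observed-case rate is not proof of bias. Tests may be missed for reasons unrelated to response, such as the pandemic-prevented visits foreseen in Protocol 5.1, and counting those as failures has its own distortion.
- A partial-test rule may exist where it cannot be read. The SAS code in Appendix A1 is redacted, and the Laboratory Manual and Protocol Deviation Assessment Plan were not available.
- The remark in SAP 5.7.2.2 about imputed values is qualified as applying only where applicable, so it promises none in the primary analysis.

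**Conclusion.** No change follows. Followed as written, the plan gives an observed-case primary rate, an all-treated rate with missing counted as failure, a per-protocol rate, a listing of missing endpoints and the reasons for exclusion. A reader can see both estimates and the children who separate them. The gap could be about 8 points with 3 untested children and 11 with 4. Those counts are assumptions, and the gap would be visible in the planned outputs.

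Making the imputed ITT rate primary would be a trade-off, with no clear gain. It fits poorly with sizing on 28 evaluable children and counts non-drug absences as failures. It would also be open to challenge as a late change in an open-label study: SAP version 2.1 is dated 5 March 2022, and the main study was planned to end in the first quarter of 2022.

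What remains is detail that analysts can fill sensibly: reading SAP 5.7.1.2 together with 5.7.2.3, and classifying any partial test, including whether T0 counts towards the peak, at the data review before database lock (SAP 5.3). This conclusion rests on the study staying descriptive, as Protocol 11.3 states, and on partial tests being few.

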### 5.1.2 *Descriptive Statistics*

All raw and derived variables will be listed and described using summary statistics. For categorical variables, summary statistics will be displayed using descriptive statistics by frequency count and percentages by category. The missing category will be presented if there is at least one missing category for at least one gender group. Except otherwise specified, participants with missing data will be included in the calculation of percentages. For quantitative variables, summary statistics will be displayed using descriptive statistics by number of observations, mean, standard deviation (SD), median, minimum and maximum. Missing data will be displayed.

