### 5.7.3.2 *Secondary Analysis*

For secondary efficacy endpoints related to a change at Month 3, 6 compared to baseline, the descriptive summary statistics (number of participants (n), mean, SD, median, quartiles, minimum, maximum) will be calculated on the mITT.

Exact two-sided 90% CI will also be constructed for all secondary endpoints expressed as proportions.

GV cm/y, Height, Weight, BMI, FSH, LH values, Bone age, difference between Chronological age and Bone age, mean Oestradiol/Testosterone, Uterine Length and Testicular Volume over time will be graphically presented via individual observed values (scatter) as well as mean and standard deviation of the observed values (Baseline, Month 3, and Month 6).

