### 5.7.3.3 *Sensitivity Analysis*

Secondary efficacy endpoints will be performed on the PPS using the same statistical method as mITT.

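### The SAP and protocol Section 11 specify no Month 6 LH suppression rate for all treated children, although the protocol synopsis names the ITT for secondary endpoints

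*SAP*

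**What the plan says.** **Sets.** The mITT (SAP 4; same in Protocol 11.1) is "All treated participants having at least one baseline and at Month 3 post-baseline assessment of the primary efficacy endpoint". The PPS is the mITT less children with relevant major deviations. The ITT needs only one dose.

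**Month 6 LH suppression.** This is a secondary endpoint. SAP 4.1 states: "The secondary efficacy analyses will be based on the mITT population". SAP 5.7.1 and Protocol 11.1.1 and 11.3 agree. SAP 5.7.3.3 adds: "Secondary efficacy endpoints will be performed on the PPS using the same statistical method as mITT". SAP 4.1 and 5.7.1 make that PPS analysis optional. For the interval, SAP 5.7.3.2 says: "Exact two-sided 90% CI will also be constructed for all secondary endpoints expressed as proportions".

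**Missing results.** SAP 5.7.1.2: "A NRI method will be used for missing LH response and FSH response at month 3 or month 6". The general rule in SAP 5.1.2 is: "The missing category will be presented if there is at least one missing category for at least one gender group". The same section has missing data displayed for quantitative variables.

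**Other GnRH-test visits.** At Month 3 the primary endpoint is repeated "with the same statistical method using NRI method on the ITT set" (SAP 5.7.2.3), and SAP 5.7.2.2 adds: "A listing will be provided including all participants with missing values for the primary endpoint". For the extension phase, which includes Month 12, SAP 4.1 uses the ITT and PP sets.

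**Synopsis.** Under Statistical Methods, the protocol synopsis gives ITT, mITT and PP as the sets for both primary and secondary efficacy endpoints. It then puts the change-from-baseline summaries on the mITT, with the PP optional. SAP 2.6 reports no departure from the protocol's statistical section.

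**The concern.** A Month 3 entry condition suits a Month 3 endpoint. Carried over to Month 6, it selects children on having completed an earlier visit, and NRI cannot restore a child who is outside the set. The only sensitivity set, the PPS, narrows the population further.

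Month 6 suppression is the first-listed secondary objective and will be read beside Month 3. Under the SAP it is the only post-baseline GnRH-test visit without an ITT rate. A reader who wants the proportion of all treated children known to be suppressed at Month 6 would have to work it out. Within the mITT, the single imputed percentage also counts a missed test and an unsuppressed test alike.

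**Working it through.** **Inputs.** The plan states no sample size or precision for the Month 6 rate. Its Month 3 sample size reproduces: with n = 28, null 70% and one-sided 0.05, the exact test rejects at 24 or more responders (exact alpha 0.0474), with power 0.858 at 90% (stated: 85%). Inflation gives 28/(1 − 0.10) = 31.1, rounded up to 32. I take 32 treated, about 90% suppressed among those tested, and up to 32 − 28 = 4 lost. The split of losses over time is my assumption.

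**1. Losses before Month 3 only.** Let b children have neither a Month 3 nor a Month 6 test, and let x of the rest be suppressed at Month 6.

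- mITT rate = x/(32 − b)
- ITT-NRI rate = x/32
- gap = x·b/[32(32 − b)]

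| b | mITT (exact 90% CI) | ITT-NRI (exact 90% CI) | Gap, points |
|---|---|---|---|
| 0 | 29/32 = 90.6% (77.5–97.4) | 29/32 = 90.6% (77.5–97.4) | 0 |
| 1 | 28/31 = 90.3% (76.8–97.3) | 28/32 = 87.5% (73.6–95.6) | 2.8 |
| 2 | 27/30 = 90.0% (76.1–97.2) | 27/32 = 84.4% (69.9–93.6) | 5.6 |
| 3 | 26/29 = 89.7% (75.4–97.1) | 26/32 = 81.3% (66.3–91.5) | 8.4 |
| 4 | 25/28 = 89.3% (74.6–97.0) | 25/32 = 78.1% (62.8–89.3) | 11.2 |

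If no tested child changes status, Month 3 has the same fractions, so SAP 5.7.2.3 already reports this gap there. The row b = 4 puts every planned loss before Month 3 and is the upper end.

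**2. Losses after Month 3.** Take 1 child lost before Month 3 and 2 lost after it, both suppressed at Month 3, with no tested child changing status.

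| Basis | Month 3 | Month 6 | Change, points |
|---|---|---|---|
| mITT with NRI | 28/31 = 90.3% | 26/31 = 83.9% | −6.45 |
| ITT with NRI | 28/32 = 87.5% | 26/32 = 81.3% | −6.25 |
| Observed cases | 28/31 = 90.3% | 26/29 = 89.7% | −0.7 |

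Missed tests alone produce the fall on both imputed bases, so an ITT-NRI row does not by itself separate missing from unsuppressed. Observed cases can mislead the other way: if the 2 later losses were unsuppressed, that rate rises from 28/31 to 28/29, by 6.2 points. Over every split of up to 4 losses, missing data alone change the imputed rates by a fall of 0 to 12.5 points, and the observed-case rate by anything from a 1.3-point fall to a 9.7-point rise.

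**3. Can the missing count be recovered?** Yes, on the mITT. In step 2 the planned table of change in peak LH would show n = 29 at Month 6 out of 31. The suppression table gives 26 suppressed and 31 − 26 = 5 counted as not suppressed. Of those 5, 31 − 29 = 2 are missing and 3 were tested and unsuppressed. NRI leaves the numerator alone, so 26/29 follows directly.

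**4. Direction.** If 2 children miss only the Month 3 test, the mITT gives 27/30 = 90.0%, while all 32 tested at Month 6 give between 27/32 = 84.4% and 29/32 = 90.6%. The mITT rate is not always the higher one.

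**The case against.** The other side has four good arguments.

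- **The report already shows who is missing.** A reader might infer that a fall from Month 3 could never be traced to missed tests. The documents do not support that. SAP 5.1.2 displays missing data for quantitative variables, SAP 5.7.3.2 gives the n for change in peak LH and plots individual LH values, SAP 5.7.1 lists all efficacy data, and SAP 5.2 tabulates reasons for exclusion from each set. This stands. What remains is that no Month 6 ITT rate or interval is specified, and that the SAP does not say whether a missing category appears beside an imputed response.
- **A child tested at Month 6 but not at Month 3 should be rare.** One might point to the remote COVID visits in Protocol 5.1. It is only an assumption that such a child misses the GnRH test and stays in the study. Per Table 1, the Month 3 test precedes the second injection at the same visit, so a child seen remotely would ordinarily miss that too. Efficacy assessments are also tied to the time since the last dose. The main excluded group is therefore early dropouts.
- **The gap repeats Month 3.** This is true when all losses precede Month 3, and the exclusion counts let a reader rescale to 32.
- **One fixed set with conservative imputation at both visits is defensible, and Month 12 is a weak precedent.** The extension is optional, and the NRI rule names only Months 3 and 6. Both are fair, which is why the mITT should stay the main set.

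A reader might also infer that the ITT is planned nowhere for this endpoint. The synopsis says otherwise, so the point is limited to the SAP and protocol Section 11, together with their unreconciled conflict with the synopsis.

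**Conclusion.** The point holds as a cheap improvement. Following the SAP and protocol Section 11, every specified Month 6 LH suppression rate leaves out treated children without a Month 3 test, while the synopsis names the ITT for the same endpoint. With 32 treated, about 90% suppression and 1 to 4 children lost before Month 3, the mITT rate lies 2.8 to 11.2 points above ITT-NRI. It equals ITT-NRI if nobody is missing. The number and timing of losses are assumptions, since the documents give only the overall 10% dropout.

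The endpoint is secondary and descriptive. No test or sample size changes, and the primary Month 3 result is already covered by its own ITT analysis and missing-case listing.

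A reader might go further and expect a comparison restricted to children tested at both visits to isolate real change. It does not: it conditions on staying in the study, and Protocol 4.4 lists lack of efficacy among the reasons for leaving.

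**What to change.** In SAP 5.7.3.3 add: *Month 6 LH suppression will also be summarised (n, %, exact 90% CI) on the ITT with NRI, and as observed cases among ITT participants with a Month 6 GnRH test, with the number missing shown.*

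Keep the mITT as the main set. Reconcile the synopsis with Protocol 11.1.1 and SAP 4.1 so that all three name the same sets for secondary endpoints. A row for children tested at both Month 3 and Month 6 is optional, and if shown it must be labelled as describing only children who stayed.

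The cost is one SAP sentence, an alignment of the synopsis and a few table rows, with no new data. The downsides are a possibly lower companion percentage and more than one rate for a descriptive secondary endpoint, so the text should say which is the main one.
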